5.4.4. Cost-effectiveness analysis

The aim of this economic evaluation is to assess the cost-effectiveness of internal plate fixation in comparison with external fine-wire fixation for the treatment of Type C pilon fractures of the distal tibia. Therefore a cost-effectiveness analysis will be conducted as part of this trial. Costs and health outcomes associated with the surgical interventions will be collected over the follow-up period of the trial. The perspective of the analysis will be that of the National Health Services (NHS) and Personal Social Services (PSS).

The primary outcome for the economic analysis will be the additional cost per quality-adjusted life year gained of internal plate fixation compared to external fine-wire. Hence the value for money will be estimated in terms of cost per QALY following an intention-to-treat approach. Data on resource use and health outcomes will be collected prospectively during the analysis using self-reported questionnaires at baseline, 3, 6, 12 and 24 months and hospital CRFs. A discount rate will be applied to all costs and QALYs accrued after 12 months at a rate of 3.5% per annum in line with NICE guidance [47].

If the results deem appropriate (i.e. there is a non-dominant situation in the trial based evaluation) we will carry out a secondary analysis to explore how the differences observed during the trial evolve beyond the study. For this projection, we will use a decision modelling approach to extrapolate the cost-effectiveness data observed in the ACTIVE trial to a life time horizon. The analyses will be based on a combination of observed in-trial cost and HRQoL and projections of life expectancy. In the model, each patient will assume to encounter an annual risk of death based on age and sex obtained from UK life tables.

Self-reported questionnaires, including attendance at physiotherapy and hospital forms will be specifically designed to collect information on hospital stay (initial and subsequent inpatient episodes, outpatient hospital visits and A&E hospital admissions); primary care consultations (e.g. GP, nurse and physiotherapy); out-of-pocket costs and work impact of both interventions as well as return to work. The cost of each type of surgery and related complications will be essential for the analysis. Hence an accurate record of procedures at hospital level (e.g. centres in the trial) will be put in place in order to record per patient information (e.g. surgical procedures, complications related to the surgical intervention, other medical complications). Costs relating to surgical procedures will be based on time in theatre, staff time, consumables and devices, and nights in hospital after the procedure. These data will be collected via a surgical form that will be specifically designed for this trial. In order to describe the resource impact of re-operations in this clinical area, we will also collect Healthcare Resource Groups on discharge

for each admission. Similarly we will ask patients for consent to access Hospital Episode Statistics (HES) data in case it is deemed appropriate to monitor long term hospital care related to their initial injury and its treatment. Unit costs will be derived from established national costing sources such as NHS Reference Costs, PSSRU Unit costs of health and social care, and the British National Formulary. Unit costs will be multiplied by resource use to obtain a total cost for each patient. As already stated the EQ-5D-5L questionnaire will be also included in the questionnaires to measure the impact of the intervention on patient's health related quality of life. We will present descriptive statistics of the utility scores for both trial arms at each data collection point. The raw EQ-5D scores according to domain will be displayed, in order to examine the movements between levels for each domain according to the trial arm. The overall difference in EQ-5D index scores between the two arms will be examined through regression methods, consistent with the model selected in the statistical analysis. The EQ-5D health states will be valued using a UK-based social tariff. QALYs will be calculated by plotting the utility scores at each of the three time points and estimating the area under the curve [48].

For the analysis, regression methods will be used as this allows differences in prognostic variables. The pattern of missing data will be analysed and handled by means of multiple imputation (MI)[49]. A range of sensitivity analysis will be conducted to test the robustness of the results under different scenarios, including probabilistic sensitivity analysis. In case of positive results of the trial, we will recommend that costs and outcomes will be extrapolated and modelled over a longer time horizon than captured by the trial (e.g. lifetime of the patient).

Full analyses will be detailed in a Health Economic Analysis Plan (HEAP).

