4.4.2. Secondary outcomes

- 1. Olerud and Molander Ankle Score (OMAS): The OMAS is an established validated nine-item, patient-reported outcome measure developed and validated for use in clinical trials assessing symptoms following ankle fracture [35]. It contains nine items: pain, stiffness, swelling, stair climbing, running, jumping, squatting, supports and work/activities of daily living. Item responses are each scored from 0 to 25, with 0 representing the most severe state. The scale scores representing each dimension are produced by summing the responses to each item within that dimension. Raw scale scores are then converted to a metric (0-100; 0=most severe) [35]. The OMAS will be collected once at baseline (patients will be asked to complete it thinking about the week before ankle fracture) and then at 3, 6, 12 and 24 months follow-up.
- 2. *EuroQol 5 Dimensions (5L) Score (EQ5D-5L):* The EQ-5D-5L measures health-related quality of life in terms of 5 dimensions: mobility, ability to self-care, ability to undertake usual activities, pain and discomfort, anxiety and depression. Each dimension has five possible responses (no problems, slightly problems, moderate problems, severe problems and unable or extreme problems). The EQ-5D-5L will be scored according to the User Guide [36]. EQ-5D-5L data will be collected twice at baseline: *i.e.* once to assess patient health related quality of life on the day (after the injury) and once with regard to patient health related quality of life during the week before injury; then once each at 3, 6, 12 and 24 months. At baseline, the EQ-5D-5L will be collected before randomisation by patients who have capacity to consent at that time; or at the earliest opportunity after randomisation, by patients who consent having regained capacity.
- 3. *Complications:* Data on all further surgical procedures and other complications, e.g. deep wound infection (using Centres for Disease Control and Prevention definition), superficial infection, pin site infection (defined using the 'Good, Bad and Ugly' pin site grading system [37]), rehospitalisation, blood clots, wound dehiscence, septic arthritis, secondary interventions for non-union and all other secondary procedures will be

- collected by Research Nurses using CRFs for infections and hospital records at 3, 6, 12 and 24 months.

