4.9. Follow up

Participants will be followed up at 3, 6 and 12 months post-randomisation. The primary follow-up point is 12 months post-randomisation. We will have an additional secondary outcome endpoint of 24 month follow up for all patients recruited except for those in the last year of the recruitment period. This will enable us to gather data for the secondary outcomes and economic analysis, whilst reducing costs and total length of the trial by 12 months. All follow-up will be undertaken through postal questionnaires. Follow-up data of patient questionnaires may also be collected at 3, 6, 12 and 24 months in NHS clinics where follow-up clinics form part of routine care, as necessary. Radiographs are those routinely used for the investigation of patients with a suspected fracture of the distal tibia and for the follow-up of such patients following any intervention, so there will be no need to request any additional or special investigations.

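### The protocol computes QALYs from three unnamed time points, but EQ-5D-5L is scheduled at five and the same section counts QALYs beyond 12 months

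*Protocol*

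**What the plan says.** The rule is in Protocol section 5.4.4: "QALYs will be calculated by plotting the utility scores at each of the three time points and estimating the area under the curve". The points are not listed.

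Other parts of the protocol describe a longer schedule:

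- Section 4.4.2: "EQ-5D-5L data will be collected twice at baseline" (once for the day itself, after the injury, and once recalling the week before it), and "then once each at 3, 6, 12 and 24 months". Table 1 shows the same five occasions.
- Section 5.4.4, on the data for the economic analysis: "self-reported questionnaires at baseline, 3, 6, 12 and 24 months and hospital CRFs".
- Section 5.4.4, on the horizon: "Costs and health outcomes associated with the surgical interventions will be collected over the follow-up period of the trial".
- Section 5.4.4, on discounting: "A discount rate will be applied to all costs and QALYs accrued after 12 months at a rate of 3.5% per annum".
- Section 4.9 opens with "Participants will be followed up at 3, 6 and 12 months post-randomisation". It then adds a 24-month assessment for everyone except those recruited in the last year of recruitment, and says this assessment is there for the secondary outcomes and the economic analysis.

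Section 5.4.4 leaves the full economic analysis to a separate Health Economic Analysis Plan, which is not at hand. It also says that missing data will be handled by multiple imputation.

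**The concern.** Additional cost per QALY gained is the primary outcome of the economic evaluation, and cost-effectiveness is part of the trial's stated aim. The QALY rule should therefore agree with the data collected and with the horizon over which costs are counted. As written it agrees with neither.

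An analyst who follows the sentence must choose three of the five points without guidance. Different choices change the period covered, the shape of the recovery curve, or both. Under some choices, costs and QALYs would refer to different periods, and there would be no second-year QALYs for the discounting rule to act on. The choice could also be made after the utilities have been seen, which a prespecified plan should prevent.

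**Working it through.** **1. Count the points.** Section 4.4.2, Table 1 and section 5.4.4 agree on months 0, 3, 6, 12 and 24: five time points, four of them follow-ups. Baseline has two measurements at one time point. The stated figure of three cannot be reproduced:

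- All scheduled points: 5.
- All follow-ups without baseline: 4.
- Baseline to 12 months, which is the schedule for last-year recruits: 4.
- The list of 3, 6 and 12 months that opens section 4.9: 3, but this omits both baseline and 24 months.

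The last of these may be where the number came from. The document does not say so.

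**2. What a three-point curve discards.** It leaves out 5 − 3 = 2 collected utilities for participants with 24-month follow-up, and 4 − 3 = 1 for last-year recruits.

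**3. Period covered.** Span = last point minus first point.

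- 3, 6 and 12 months: 12 − 3 = 9 months, and 9/24 = 37.5% of follow-up. Months 0–3 and 12–24 (15 months) carry no QALYs.
- Baseline, 12 and 24 months: 24 of 24 months, but the first year becomes a straight line and the 3- and 6-month values are not used.

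**4. Does the direction of the error follow?** For differences d(t) in utility between arms, the incremental QALY is the sum over adjacent points of [d(a) + d(b)]/2 × (b − a)/12. In months, the trapezoid weights are:

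- Five points: 1.5, 3, 4.5, 9 and 6 at 0, 3, 6, 12 and 24.
- 3/6/12: 1.5, 4.5 and 3.
- 0/12/24: 6, 12 and 6.
- 0/6/24: 3, 12 and 9.

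The document gives no utility differences, so the three profiles below are assumptions chosen to show the range. They are undiscounted, with no difference at baseline.

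| Assumed difference at 3, 6, 12, 24 months | Five points | 3/6/12 | 0/12/24 | 0/6/24 |
|---|---|---|---|---|
| Early only: 0.10, 0.05, 0, 0 | 0.044 | 0.031 | 0.000 | 0.050 |
| Constant: 0.05 throughout | 0.094 | 0.038 | 0.075 | 0.088 |
| Late only: 0, 0, 0, 0.10 | 0.050 | 0.000 | 0.050 | 0.075 |

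Two cells worked through:

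- Early only, five points: (3 × 0.10 + 4.5 × 0.05)/12 = 0.525/12 = 0.044.
- Late only, 0/6/24: 9 × 0.10/12 = 0.075.

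Against the five-point value, a three-point curve can be lower, higher or unchanged.

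**5. Which horizon does the rest of the text imply?** The discounting sentence has an effect only if QALYs after 12 months are counted. Section 4.9 assigns the 24-month data to the economic analysis. Section 5.4.4 also plans descriptive utilities by arm at every collection point. All three indicate a 24-month curve through all scheduled values.

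**The case against.** The best defence is that this is leftover or mistaken wording. The surrounding text points to a 24-month analysis, and the Health Economic Analysis Plan will give the detail. Most of that stands. A slip is more plausible than a deliberate nine-month curve. The evaluation is separate from the primary DRI analysis, which is unaffected. Which baseline value starts the curve is a detail that could fairly be left to the later plan.

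The defence does not remove the contradiction. The protocol is not silent here: it states a number, and the number conflicts with its own schedule. The later plan must either repeat the error or depart from the protocol.

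A reader might go further and infer that the trial will omit part of follow-up, or that cost per QALY will be inflated by some factor. The document supports neither inference. The points are unnamed, and at least one set of three (baseline, 12 and 24 months) spans the full period. The discounting sentence argues against truncation. Any multiplier on the cost-effectiveness ratio would come from an invented utility profile and one chosen subset, and the table shows that the sign itself is not fixed. The claim that the arms differ mainly early is also not established: the protocol's background describes frame inconvenience and pin-site infection, but also deep infection, arthritis, amputation and long-term disability.

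**Conclusion.** The inconsistency is certain. Section 5.4.4 computes QALYs from three points, while the protocol schedules five (four for last-year recruits) and plans to count and discount QALYs beyond 12 months. Any three-point rule discards collected utilities from the primary economic outcome.

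The numerical consequence is not determined by the document. The coverage figures (9 of 24 months for 3/6/12, all 24 for baseline/12/24) follow directly from the schedule. The incremental QALYs in the table rest on assumed profiles and show only that the error may be downward, upward or nil. The point should be corrected before the economic analysis, but it does not threaten the trial's main clinical comparison.

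**What to change.** Replace the sentence in section 5.4.4, and carry the same text into the Health Economic Analysis Plan, with wording to this effect:

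> QALYs will be the trapezoidal area under each participant's EQ-5D-5L utility curve, from the after-injury baseline value (time zero) through the values at 3, 6, 12 and 24 months. The recalled pre-injury value will not be used as time zero.

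The pre-injury recall describes a state that had ended before randomisation, so it cannot start a curve of time lived after it.

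Add a rule for participants recruited in the last year, who have no planned 24-month assessment. Either of these would serve:

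- Use their baseline to 12-month values as observed, and handle year 2 with the multiple imputation that section 5.4.4 already plans.
- Report a 12-month analysis of all participants alongside the 24-month one.

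The rule matters in practice. Section 4.5 assumes that, under the revised target, 80% of those in the primary analysis reach 24 months, so about one in five would have no observed second year.

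The cost is two or three sentences. All the values needed are already scheduled, and neither the sample size nor the DRI analysis changes.

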5.4.5. Qualitative analysis

We will use NVivo software to assist our organisation of the qualitative analysis. To achieve a systematic approach to data analysis we will engage in: detailed familiarisation; identification and indexing of key themes; contextualising these themes in relation to the broader dataset; and interpreting them with a focus on addressing the specific aims of the study:

- Are surgeons willing to randomise eligible patients and adhere to randomisation to internal or external fixation?
- What are patients' experiences of being approached to participate in the trial?
- Are patients willing to be randomised in a trial comparing the two treatments?

 What are the barriers to successful delivery of the future trial and how can they be overcome?

Initially following transcription, the interview material will be organised according to analytical headings using a constant comparison approach [50]. We will combine coding with a holistic consideration of transcripts to retain the context of participants' narratives whilst accounting for deviations. Data from consultation recordings will also be analysed thematically and integrated with interview data. During the analysis, regular meetings will be held between the research team, and PPI participants where appropriate, to discuss the emergent themes from the qualitative interviews and consultation recordings. Findings from the qualitative work will be integrated with the pilot RCT outcomes in order to inform the design of a full-scale RCT.

5.5. Data monitoring

The primary responsibility for monitoring the safety of participants in clinical trials lies with the trial Sponsor. Data monitoring will be undertaken by the Trial Management Group (TMG), Trial Steering Committee (TSC) and a Data Monitoring and Ethics Committee (DMEC), on behalf of the Sponsor and Funder. The project will also be monitored by the Sponsor for whom a representative will be invited to attend the Trial Management Group and Trial Steering Committee meetings and we will submit regular progress reports to the Funding Body.

5.5.1. Trial Management Group (TMG)

A TMG has been established to oversee the day-to-day management of ACTIVE, and is chaired by the Chief Investigator. Other members include the trial statisticians, trial manager, trial coordinators, health economist, qualitative researcher and other co-applicants. The role of the TMG is to monitor all aspects of the conduct and progress of the trial, ensure that the protocol is adhered to and take appropriate action to safeguard participants and the quality of the trial itself. The TMG will meet monthly by teleconference, with quarterly face-to-face meetings where feasible, from the start of the study until the end of the pilot. The TMG will meet more frequently if there is a need to monitor recruitment more closely. The TMG will then meet quarterly.

5.5.2. Trial Steering committee (TSC)

An independent TSC has been established to provide overall supervision for ACTIVE on behalf of the Sponsor and Project Funder and to ensure that the project is conducted to the rigorous standards set out in the Department of Health's Research Governance Framework for Health

and Social Care and the Guidelines for Good Clinical Practice. This committee comprises of an Independent Chair who is a Professor of Health Services Research and Clinical Trials, a consultant orthopaedic surgeon with expertise in surgically fixing pilon fractures, a public contributor, the Chief Investigator and Trial Coordinator/Manager. Other study collaborators may also attend the meeting with the agreement of the Chair. The TSC will meet at least annually and will work to a Charter which has been agreed.

5.5.3. Data monitoring and ethics committee (DMEC)

The role of the DMEC is to review accumulating data in ACTIVE and advise the sponsor (directly or indirectly) on the future management of the trial. The DMEC is Chaired by a statistician, with other members comprising of experts in the clinical area. The DMEC will review safety and efficacy data as well as quality and compliance data. The DMEC will review all serious adverse events which are thought to be treatment related and unexpected. The independent members of the DMEC committee will be allowed to see unblinded data. The DMEC will meet at least annually or more frequently if the committee requests. A DMEC Charter has been agreed which they will work to.

6. Harms

6.1. Risks and anticipated benefits

In the context of the lack of robust evidence to determine the best surgical intervention for patients with these injuries, the risks are not increased through trial participation. However, there are risks associated with this study, which are predominantly the risks associated with the surgery: infection, bleeding and damage to the adjacent structures such as nerves, blood vessels and tendons. Participants in both groups will undergo surgery and will potentially be at risk from any/all of these complications.

In this trial surgeons will perform interventions which they undertake as part of routine practice and with which they are familiar. Measures taken by us, such as our emphasis on good practice and standardised protocols/care pathways throughout, are likely to reduce risk and could bring additional benefits. We will adhere to the Research Governance Framework/ UK Policy Framework for Health and Social Care Research and MRC Good Clinical Practice Guidance [51, 52] [53]. The participant information sheet for the study will be developed with the involvement of service users and will give a balanced account of the possible benefits and known risks of the

interventions. It will state explicitly that quality of care will not be compromised if the participant decides to a) not enter the trial or b) withdraw their consent. We will make it clear that there is no obligation to participate. Written informed consent will be obtained from all participants after they have had sufficient time to read the study materials and ask questions. Whilst we will recruit participants who do not have capacity to consent via a professional or personal consultee, we will not recruit patients who do not have the capacity to understand the instructions for treatment. An application for NHS ethical approval will be made. We do not anticipate major ethical concerns with this study. The only potential concern would be the inclusion of patients who lack mental capacity to understand instructions for treatment. We will allow the treating clinician to exclude these patients from this trial. The local R&D committee of each of the participating hospitals will approve local involvement in the trial. The trial will be subject to DMEC and TSC oversight.

6.2. Informing potential trial participants of possible benefits and known risks

Informed consent will be obtained by the trained local research nurse or clinician using a patient information leaflet developed with the help of service users, which explains the risks and benefits clearly. In the unlikely event that new information arises during the trial that may affect participants' willingness to take part, this will be reviewed by the TSC for addition to the patient information leaflet. A revised consent form will also be completed if necessary.

6.3. Adverse event management

Adverse events (AE) are defined as any untoward medical occurrence in a clinical trial participant and which do not necessarily have a causal relationship with the treatment. We will only collect adverse event data related to treatment for the original injury, that are 'unexpected' and only up until the 24 month follow up. All AEs will be listed on the appropriate Case Report Form for routine return to York Trials Unit. Serious adverse events are defined as any untoward and unexpected medical occurrence that: 1) Results in death; 2) Is life-threatening; 3) Requires hospitalisation or prolongation of existing inpatients' hospitalisation; 4) Results in persistent or significant disability or incapacity; 5) Is a congenital anomaly or birth defect; 6) Any other important medical condition which, although not included in the above, may require medical or surgical intervention to prevent one of the outcomes listed. A list of expected adverse events that we will not report is given in Table 2. This is because these are well known complications

that will be recorded on other CRFs for the two routine surgical treatments that the specialist clinical care teams will be experienced in managing.

Table 2: Expected adverse events

Wound complications (e.g. delayed healing)
Infection at the surgical site or adjacent joint
Pin site infection requiring procedure, antibiotics or admission
Damage to a nerve or blood vessel
Breakage of orthopaedic hardware
Thromboembolic events
Secondary operations for or to prevent infection, malunion, non-union or
for symptoms related to the metalwork.
Wire breakage and removal / exchange of wire
Partial / complete frame removal
Chronic Regional Pain Syndrome
Amputation
Elective admissions to hospital for the ankle
Abnormal blood results related to an infection

All serious adverse events (SAE) will be entered onto the Serious Adverse Event reporting form and faxed to a dedicated fax machine at York Trials Unit within 24 hours of the investigator becoming aware of them. Once received, causality and expectedness will be confirmed by the Chief Investigator. SAEs that are deemed to be unexpected and related to the trial will be notified to the Research Ethics Committee (REC) and sponsor within 15 days. All such events will be reported to the Trial Steering Committee and Data Monitoring Committee at their next meetings. Follow up reports a month later will be reviewed by the CI to ensure that adequate action has been taken and progress made.

7. Research ethics approval

As the study is led from England, an application for NHS ethical approval in England will be made and we will also apply to the Health Research Authority (HRA) for governance approval. Local R&D will confirm the capacity and capability of centres to participate. We do not anticipate major ethical concerns with this study. The only potential concern would be the inclusion of patients who lack mental capacity to understand the trial treatment. We will allow the treating clinician to exclude these patients from this trial.

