4.2.1. Inclusion criteria

- Patients aged 16 years or older
- With a closed intraarticular pilon fracture of the distal tibia classified according to AO: AO
 43 Cl, C2 and C3 (complete articular). This includes patients with a bi-lateral pilon fracture and who have polytrauma.
- Where the treating surgeon believes the patient will benefit from surgical fixation

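### Section 6.3 conflicts with itself on whether deaths unrelated to treatment are collected, and the protocol nowhere commits to recording every death with its date

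*Protocol*

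**What the plan says.** Section 6.3 contains rules that do not fit together.

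- **Definition of an adverse event.** It covers occurrences "which do not necessarily have a causal relationship with the treatment".
- **Collection rule.** "We will only collect adverse event data related to treatment for the original injury, that are 'unexpected". Both conditions apply: related and unexpected. The collection window closes at 24 months.
- **Definition of a serious event.** "Serious adverse events are defined as any untoward and unexpected medical occurrence that: 1) Results in death". There is no relatedness condition here, but the event must be unexpected.
- **Reporting rule.** "All serious adverse events (SAE) will be entered onto the Serious Adverse Event reporting form", within 24 hours of the investigator learning of them. The Chief Investigator confirms causality and expectedness after receipt.
- **Expected events.** Table 2 lists complications that will not be reported as adverse events because other CRFs record them. The list includes thromboembolic events and infection at the surgical site. It makes no exception for a fatal outcome.
- **Onward reporting.** Section 6.3 sends to the ethics committee and sponsor, and then to the TSC and DMEC, the serious events judged unexpected and related. Section 5.5.3 says: "The DMEC will review all serious adverse events which are thought to be treatment related and unexpected".

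On the population, section 4.2.1 states: "This includes patients with a bi-lateral pilon fracture and who have polytrauma". Section 4.6 includes intensive care among the places of recruitment, and section 7.2.2 allows enrolment through a consultee in some of the countries.

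Death is not among the outcomes in section 4.4 or the items in Table 1. For the economic analysis, section 5.4.4 says: "The pattern of missing data will be analysed and handled by means of multiple imputation (MI)[49". It gives no rule for participants who die and leaves the full analysis to a Health Economic Analysis Plan (HEAP).

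**The concern.** Some participants will have other serious injuries, so deaths that have nothing to do with the ankle surgery can be foreseen. Whether such a death enters the trial data depends on which sentence of 6.3 a site follows. Whether a death after a listed complication is reported depends on whether expectedness is judged for the complication or for the death. Clinicians who know the allocation make the first judgement in both cases.

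Two things are at stake. The first is safety monitoring: all-cause mortality by arm is the comparison least open to judgement about cause, and no stated route guarantees that it reaches the DMEC. The second is the economic analysis: QALYs and costs need the date of death, and an analysis plan written later cannot recover a date that was never collected.

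**Working it through.** **Step 1: trace three kinds of death through the stated rules.**

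| Death | Collection rule (6.3) | Serious-event definition and reporting rule (6.3) | Expressly sent to DMEC (5.5.3, 6.3) |
|---|---|---|---|
| Unrelated to treatment, not expected (e.g. from another injury) | Not collected | Reported within 24 hours | No |
| Related to treatment, through an event in Table 2 | Not collected if classed as expected | Outside reporting if classed as expected; inside if the death itself counts as unexpected | No, if classed as expected |
| Related and unexpected | Collected | Reported | Yes |

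Only the last row is consistent. The first row is a direct conflict. The second is unclear, because Table 2 lists the complications but not death itself.

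**Step 2: look for any other commitment to record death.** Section 4.4.2 has research nurses collect complications from CRFs and hospital records at 3, 6, 12 and 24 months. Section 4.9 describes a system that tracks study status. Section 5.4.3 summarises withdrawals, with reasons where these are known. Each may bring a death to light, but none requires the fact and date of death for every participant. Section 7.2.3 withdraws those who have not regained capacity at 3 months, so an early death in that group could be coded as a withdrawal. Patient follow-up is mainly postal (4.9), so a death unknown to the site would first appear as non-response.

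**Step 3: illustrate the QALY consequence.** The protocol has no figure to reproduce: it gives neither a death rate nor utilities. The inputs from the protocol are 125 participants per arm (4.5) and discounting at 3.5% a year after 12 months (5.4.4). The assumed inputs are death at one month, a constant imputed utility *u* of 0.5 to 0.7, and every such death imputed as a survivor.

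QALYs wrongly credited per death over 24 months = *u* × 11/12 + *u*/1.035.

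- *u* = 0.5: 0.458 + 0.483 = 0.94
- *u* = 0.7: 0.642 + 0.676 = 1.32

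Effect on the mean of one arm, per death: 0.94/125 = 0.0075 to 1.32/125 = 0.0105.

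Effect on the difference between arms, with three more deaths in one arm: 3 × 0.0075 = 0.023 to 3 × 0.0105 = 0.032.

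**Step 4: vary the assumptions.** For one arm's mean, undiscounted, overstatement = death risk × utility × years from death to month 24.

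- Low: 0.5% × 0.5 × 1.0 = 0.0025
- High: 4% × 0.7 × 1.9 = 0.053

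These risks correspond to about 1 to 10 deaths among 250 participants. The bias in the between-arm difference is smaller and depends on the imbalance; equal deaths in the two arms would largely cancel.

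**The case against.** The strongest reply is that the serious-event route already captures deaths. The definition names death with no relatedness condition, all such events are sent in within 24 hours, and the central judgement of cause comes only after receipt. Death is not in Table 2, so a death from another injury would count as unexpected. Hospital-record checks, status tracking, telephone and text contact with non-responders and the 12-month imaging visit would reveal others. The DMEC's remit in section 5.5.3 also covers safety data in general, its independent members may see unblinded data, and it works to a Charter that is not shown.

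Much of this stands, and it rules out three stronger readings that a reader might infer:

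- **That nothing else records death.** The serious-event definition and reporting rule contradict this. What the text shows is a conflict and the lack of an explicit commitment.
- **That the DMEC sees only events already judged related.** Its general safety remit is wider. The narrower point is that only related and unexpected serious events are expressly promised to it.
- **That multiple imputation will give participants who died a survivor's QALYs.** The protocol does not say that deaths are treated as missing, and the handling of deaths is properly left to the HEAP.

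The reply does not remove the conflict. A site that follows the collection sentence would not report an unrelated death, and a fatal Table 2 event can be filtered out as expected. The other routes are incidental.

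**Conclusion.** The point holds as a contradiction in a stated rule together with a missing commitment. Section 6.3 gives two answers on unrelated deaths and an unclear answer on deaths from listed complications, and neither kind has a guaranteed route to the DMEC by arm. This should be corrected in the protocol, because it concerns what is collected, which no later analysis plan can repair.

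The size cannot be derived from the documents. The shift of about 0.02 to 0.03 QALYs rests on assumed utilities, an imbalance of three deaths, death at one month, non-recording or treatment as missing, and 24 months of follow-up for those concerned. Death at one month is close to the most unfavourable timing. The number of deaths is unknown and may be small. No effect on the primary DRI analysis has been shown.

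**What to change.** Reconcile the collection sentence in section 6.3 with the serious-event definition and the reporting rule, and take death out of both the relatedness and the expectedness conditions. Suggested text: *Death from any cause, with date and cause, is recorded for every randomised participant to the end of their scheduled follow-up, regardless of relatedness or expectedness, and is reported to the DMEC by arm.* Add the matching line to section 5.5.3.

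Section 5.4.4 needs no analysis rule of its own, but the HEAP should be checked to confirm that deaths are not handled as missing data.

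The cost is one CRF item, completed from hospital records that research nurses already consult at 3, 6, 12 and 24 months. No treatment or visit changes.
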